### **3. Background:**

The economic and clinical toll of osteoporosis related fractures is well known. Most fractures among the aging population are at least in part related to osteoporosis and the costs for acute health care alone top \$15 billion annually. Pelvic fractures are among the most costly osteoporosis related fractures due to loss of function, long hospitalizations and rehabilitation and the difficulty in managing these fractures. Pelvic fractures can serve as a model of fracture healing for other osteoporosis related fractures. Success in this trial may also help encourage patients and doctors to initiate treatment soon after a fracture. This is important because subsequent fractures occur with greatest frequency shortly after the first fracture. The drug, rhPTH(1-34), referred to in this application as Teriparatide (TPTD), is currently marketed as a treatment for osteoporosis in men and women at high risk of fracture. Elderly patients with non-traumatic pelvic fracture have osteoporosis and are at high risk for future fracture, thus are eligible for treatment with TPTD. TPTD stimulates bone formation and remodeling with formation of new bone tissue, improved skeletal architecture, increased bone mass (i.e. a true increase in the amount of bone tissue), and potentially by periosteal bone formation, an increase in the diameter of some bones in the skeleton. A large body of evidence in preclinical models supports the concept that TPTD can improve fracture healing. In addition, daily subcutaneous injection of TPTD for bone union using local bone grafting after instrumented lumbar posterolateral fusion in women with postmenopausal osteoporosis was more effective than oral administration of bisphosphonate in an observational study. Recently, an acceleration of fracture healing with TPTD (20 mcg per day) was reported

in a randomized controlled trial of 102 postmenopausal women who had sustained a distal radial fracture. The authors concluded that their result should be interpreted with caution and noted that there was no further improvement with the 40 mcg dose. This provides rationale for our using a dose of 20 mcg TPTD per day. A recent study reported the successful use of PTH 1-84 to enhance the healing of fractures of the pubic ramus in 65 patients, based on x-ray and CT images. This study was not randomized or blinded and is therefore subject to bias, particularly since patients in the PTH 1-84 treatment group were treated at a single center, and patients from both this center and another center served as controls (no PTH 1-84 treatment). In that study, 100 mcg of PTH 1-84 (equivalent to about 40 mg TPTD) resulted in fracture healing at a mean of 7.8 weeks, and 100% of the treated group had healed at 8 weeks following PTH1-84 administration, significantly faster than the control group (9% healed at 8 weeks and 68% at 12 weeks). Results of that study need to be confirmed for several reasons. First, a randomized, controlled, blinded study is required. Second, there may be some difference between 1-84PTH and 1-34PTH, as illustrated in a small study comparing the effects of these two peptides on cortical porosity assessed by high resolution pQCT. However, it does add to the growing clinical evidence that PTH peptides may improve fracture healing and also may improve physical function (using the Timed Up and Go test). Recent reviews and case series of TPTD and fracture healing state that there is a potential benefit of TPTD but all conclude that further randomized, placebo controlled, clinical trials are warranted. An important additional question is whether the benefit of TPTD on fracture healing wanes over time. In a recent study, improved mobility was seen at 3 and 6 months but not 12 months in TPTD treated patients with unstable pertrochanteric fractures, making a longer follow-up important in the proposed trial.

In summary, pelvic fractures are costly for both the individual and society due to the lack of surgical intervention and the long time to heal, making this an ideal fracture to use in a study of fracture healing. In addition, the lack of surgical repair means that the effects of TPTD on fracture healing cannot be confounded by a surgical procedure. Although both TPTD and (1-84PTH) have been shown to lead to some improvements in fracture healing, a randomized double-blinded placebo controlled clinical trial is now needed to confirm and extend any beneficial effects of TPTD on the acceleration of fracture healing. Additionally, since the pelvic bone has a higher proportion of cancellous bone and thinner cortical walls than long bones and TPTD increases bone mass most effectively in cancellous bone, pelvic fracture might be particularly amenable to accelerated fracture healing with TPTD. The TPTD or placebo would be administered in addition to current standard of care for pelvic fractures, which includes pain management, patient mobilization, and the prevention of complications associated with comorbid conditions. Given that pelvic fractures are an osteoporosis related complication and represent severe osteoporosis, we recommend treating all pelvic fracture patients for the underlying disease of osteoporosis. Therefore, after the 3 month trial, we will offer all study participants a year of open label TPTD. Since the optimal time to initiate osteoporosis treatment is when the patient has a fragility fracture, clinicians need to know if the drug is neutral or accelerates fracture healing. If the current study clearly demonstrates enhancement of fracture healing, the fracture team will be more motivated to start osteoporosis care (currently < 20% of patients get treated). Therefore, any evidence that fracture healing is improved with TPTD would markedly change the clinical care of this fracture. Furthermore, any benefit of TPTD to healing of pelvic fractures, may serve as a model for the study of other osteoporosis fractures.

At this time, there are no currently approved drugs for fracture healing. Therefore the premises for this trial include: (1) the need for a treatment for pelvic fractures that cannot be surgically repaired, (2) the need to study fracture healing in a well-designed placebo controlled, double blind, randomized trial to determine whether the findings of Peichel et al can be confirmed (3) to determine if 1-34hPTH can improve fracture healing similarly to findings with 1-84PTH (4) to corroborate pre-clinical data, findings from case series, and trials which suggest that TPTD may accelerate fracture healing. If the results of this trial are positive with more rapid fracture healing and potentially quicker return to normal physical function; we anticipate that more pelvic fracture patients would be appropriately treated for their osteoporosis post-fracture. In addition, a positive finding may have a dramatic impact on clinical care of patients with other osteoporosis related fractures.

Preliminary and published data strongly recommend TPTD as a bone anabolic therapy to treat the underlying osteoporosis, the ultimate cause of the fracture. The patients enrolled in this trial would all be eligible for an osteoporosis treatment with TPTD being an excellent choice. We believe there will be an added benefit of TPTD beyond the treatment of osteoporosis, including radiographic evidence of accelerated fracture healing, a quicker improvement in physical function, and a faster reduction in pain. The risks associated with the study include the potential side effects of TPTD and the radiation dose from plain x-rays and CT scans.

However, during our prior NIH planning grant (U34), we developed a technique to lower the radiation exposure in this study to be lower than that typically associated with standard care.

#### **4. Study Design:**

**Overview:** In the proposed phase 2 study, we plan to evaluate if treatment with TPTD 20 mcg daily compared with identical appearing placebo, both with the standard management of non-surgical pelvic fractures (pain management, bed rest and prevention of complications from comorbid conditions), is effective in accelerating fracture healing. This is a prospective randomized, double-blinded, placebo-controlled 3 month study of the efficacy of TPTD in postmenopausal women and men  $\geq 65$  years of age with acute fractures of the pelvis. Our primary outcome is radiographic evidence of fracture healing using low dose Focus CT at 3 months. Secondary outcomes include assessment of pain and narcotic use, and assessment of lower extremity physical function at 3 months and again from 3-12 months. We will randomize 100 patients 1:1 in a blinded fashion to receive either 20mcg of TPTD subcutaneously (SC) every day or identically appearing placebo SC for 12 weeks. All patients will have ideal medical care for comorbidities, pain management and progressive mobilization. A routine clinical protocol will be followed to quickly normalize 25-hydroxyvitamin D (goal  $>20$  ng per milliliter; the current IOM guideline 2010^35) before starting treatment. All patients will receive a loading dose of vitamin D2 (at a dose of 50,000 IU given orally) following the protocol used by Lyles et al to normalize vitamin D in a clinical trial of similar patients with acute hip fracture. After the loading dose, daily supplementation with 1000 IU vitamin D will be used for the duration of the study. This will allow for patients to be recruited and to begin the trial of TPTD or placebo within 1 month of the fracture with improved 25(OH)D levels. Calcium intake will be assessed and dietary suggestions or supplementation will be used to bring total intake to approximately 1000 mg a day, slightly lower than the recommended calcium intake for women over age 50 (in order to prevent hypercalcemia).

#### **Subjects**

**Inclusion criteria:** Postmenopausal women and men  $\geq 65$  years of age with acute pelvic fractures, occurring with minimal trauma, presenting to Helen Hayes Hospital, Lenox Hill Hospital, New York Presbyterian-Queens, Hospital for Special Surgery, or New York Hospital (Cornell Medical) within one month of the onset of symptoms. Since 25% of pelvic fractures occur in men, it is important to include men in this trial. The inclusion of males will also extend the results of the Aspenberg and Peichel trials). Given that 53% of fractures have an associated injury in the posterior pelvic ring, it is important to include these multiple rami fractures. Patients that have either one or multiple pelvic fractures or sacral and pelvic fractures will be included in the study.

#### **Exclusion Criteria:**

- 1) Persons unable to complete the NRS and other surveys based on their mini-mental status score ( $\leq 18$ ; consistent with moderate and severe cognitive impairment)
- 2) Previously (prior to fracture) non-ambulatory subjects
- 3) Exclusion criteria related to contraindication or intolerance to TPTD:
  - a) Hypersensitivity to TPTD
  - b) Patients with increased risk of osteosarcoma: Paget's disease, history of radiation exposure
  - c) Patients with active hypercalcemia
  - d) Current hyperparathyroidism and other metabolic bone disease including osteogenesis imperfecta
  - e) History of multiple renal calculi or renal calculus within the last 2 years
  - f) Normal alkaline phosphatase levels will not be used as an entrance criterion because most fracture patients will have elevations due to the acute fracture. However, we will attempt to obtain lab tests from the period prior to fracture to determine if they were normal. If unexplained elevations in alkaline phosphatase are found in labs prior to the fracture we will exclude that subject.
  - g) Evidence of metastatic cancer or history of bone cancer or any active cancer other than basal or squamous cell carcinoma.

#### **Protocol:**

#### **Recruitment:**

Subjects will be recruited, during their initial hospitalization (median length of stay is 9 days) or from the emergency room or physician office from Hospital for Special Surgery/New York Hospital, Lenox Hill Hospital, New York Presbyterian Queens, or Helen Hayes Hospital. The goal will be to start treatment within one month

of fracture. Since not all pelvic fractures are hospitalized, radiologists at each institution have agreed to contact us regarding patients with pelvic fractures who are not admitted. We will recruit approximately 100 subjects (female and male)  $\geq$  65 years of age over a total of 4 years (30 in years 1, 2 and 3 and 10 in year 4) to complete 80 subjects with 3 months of treatment, to accommodate a drop-out rate of 20% in the 3 month treatment portion of the study.

**Screening and Baseline visit:** Subjects will have their screening and baseline visit during their initial hospitalization or by coming into one of the participating hospitals for a follow-up orthopedic or outpatient visit for those with documented pelvic fractures who were not hospitalized.

**Screening visit:** At the screening visit, a Mini Mental Status Exam (MMSE) will be given to be sure that the patient is capable of providing informed consent and of completing the trial. Any persons with moderate or severe cognitive impairment will be excluded (score  $\leq$ 18 of 30 points). The consent form will be reviewed and signed. A comprehensive assessment of medical history and a brief physical exam will be performed. Blood samples will be obtained and levels of creatinine, alkaline phosphatase, calcium, intact-parathyroid hormone, and 25(OH)D will be measured. Pelvic radiographs and a full CT scan will be reviewed or obtained to determine if fractures are: single rami, multiple rami fractures or sacral and pelvic fractures (healing of sacral fractures will not be assessed, although the existence of a sacral fracture with a pubic rami fracture will not exclude an individual). In addition, the fracture will be classified by amount of displacement/overriding with 3 categories: Minimal/No displacement, Mild displacement, Moderate displacement. A loading dose of vitamin D (50,000 IU) will be given in order to normalize vitamin D in this population with high prevalence of vitamin D deficiency before initiating treatment (goal within 2 weeks of the fracture). Serum calcium must be below or equal to normal for the lab. Calcium supplements or dietary modifications will be recommended as needed to bring total calcium intake to approximately 1000 mg daily. Subjects who meet all inclusion and exclusion criteria based on labs and history will be scheduled for a baseline visit. Concomitant medications and existing baseline conditions will be collected by interview. Information about the use of prior osteoporosis treatment will be obtained and recent BP use will be categorized for randomization.

**Baseline Visit:** Baseline visits will be scheduled when all results are in and within one month of fracture. Subjects will be seen in the morning after an overnight fast. Blood will be drawn and subjects will be allowed breakfast. Vitamin D supplements (1000 IU daily) will be provided to help to maintain adequate 25OHD serum levels and calcium intake will be reviewed. A blood sample will be collected at baseline and at every visit to assess calcium level for safety. Blood samples for biochemical indices of bone turnover (serum PINP for bone formation and serum CTX for bone resorption) and 25(OH)D will be obtained at baseline and every month and analyzed by batch at the Helen Hayes Hospital Regional Bone Center. Subjects will complete the lower extremity physical function tests, an Activities of Daily Living (ADLs) and SF-36 physical function survey, NRS for pain and a survey with pill count to determine narcotic use. Subjects will be randomly assigned (with separate schemes for males and females and prior BP use) to receive either TPTD 20 mcg or identically appearing placebo. Only the statistician will be aware of subject assignment and the pharmacist will distribute the appropriate TPTD or placebo medication. Subjects will be taught by the research nurse the method of daily self-administered subcutaneous injection techniques using TPTD or placebo pens, and provided written instructions for drug administration with a diary to track injections. We have extensive experience teaching subjects to administer TPTD with >90% compliance in elderly populations and subjects in the modelling recruitment phase were willing to take TPTD. Treatment will continue for the 3 months of the proposed study. Even if the fracture heals sooner, these subjects all have osteoporosis and should maintain their osteoporosis treatment for the duration of the double blind trial while other outcomes are evaluated (0 to 3 months).

**Retention:** Subjects will be called weekly during the 3 month blinded trial to monitor side effects and adverse events, and to ensure compliance with the protocol, including medication adherence.

**Follow-up visits:** All visits will occur at the center where the subject was recruited and would normally be seen, following the schedule of procedures listed in Table 2. Visits will occur every month for 3 months. At every visit a pelvic radiograph will be taken. If the radiologist notes cortical bridging on pelvic x-ray, then a confirmatory low dose Focus CT at the fracture site(s) will be performed to assess the degree of bridging at the

fracture site(s). If full union is noted at the superior and/or inferior pubic fracture site(s) by focus CT, as evaluated by both radiologists, then no further radiographs or CT scans are needed, although all other assessments will continue. The CT will be done at either Ramapo Radiology in Suffern or MRI in New City, NY. At 3 months the remaining patients who still have not healed will undergo a focused limited low dose CT to quantify the degree of cortical bridging at the end of the 3 months of placebo-controlled treatment. In addition, radiographic follow-up will continue during the open label extension for those patients who have not healed during the 3 month active treatment phase.

Blood samples to assess bone turnover and calcium levels will be collected as indicated. Subjects will be encouraged at each visit to consume enough calcium and vitamin D (1000 IU vitamin D and dietary calcium with supplements as needed) and TPTD/placebo compliance will be assessed.

At each monthly visit (0 to 3), subjects will complete the lower extremity physical function test, ADLs, SF-36, NRS for pain and a narcotic use survey and pill count (details below). This information will be recorded by a research nurse blinded to treatment status since TPTD and placebo will be identical in appearance. Lower extremity physical function test, ADLs, SF-36, NRS for pain and a narcotic use survey and pill count will be repeated at 6, 9 and 12 months visits to determine if starting TPTD immediately after fracture results in better long term changes in function and pain, although the extension will be open label with all offered TPTD and analyzed as a separate secondary outcome (3 to 12 month; see below).

**Withdrawals:** Any subject who wishes to withdraw from the study will be asked to return any study drug and, if willing, to complete the lower extremity physical function test, ADLs, SF-36, NRS for pain and a survey and pill count of narcotic use. They will also be asked to get a final x-ray and focus CT if they consent and there has not been one within a month.

**Randomization and Medication:** This study is being performed under IND 126129 with [name] as the sponsor. Within one month of the onset of symptoms, all subjects will be given either (1) TPTD or (2) TPTD- placebo for 3 months. Eli Lilly has agreed to provide TPTD and matching placebo in order to mask treatment for the double blind study. TPTD is supplied as a sterile, colorless, clear, isotonic solution in a glass cartridge which is pre-assembled into a disposable delivery device (pen) for subcutaneous injection. Each prefilled delivery device is filled with 2.7 mL to deliver 2.4 mL. Each mL contains 250 mcg teriparatide (corrected for acetate, chloride, and water content), 0.41 mg glacial acetic acid, 0.1 mg sodium acetate (anhydrous), 45.4 mg mannitol, 3 mg Metacresol, and Water for Injection. In addition, hydrochloric acid solution 10% and/or sodium hydroxide solution 10% may have been added to adjust the product to pH 4. The placebo pen contains the same solution without the TPTD. Medication pens must be refrigerated after each daily use. Compliance will be assessed by review of subject injection diaries and by weighing returned TPTD/placebo pens.

Randomization will be by gender and bisphosphonate (BP) use creating 4 randomly permuted block randomization lists. We will not exclude prior BP use, however, since the recent use of BP may impact TPTD effect, BP use will be used to create the following strata for randomization within males and females: (1) Recent BP use (greater than one year use within 2 years)/female or (2) Recent BP use (greater than one year use within 2 years)/male (3) distant or never ( $\geq 3$  years since last BP or never users)/female (4) distant or never ( $\geq 3$  years since last BP or never users)/male. We hypothesize that acceleration of pelvic fracture healing by TPTD will not be significantly affected by prior BP use because this skeletal site is largely cancellous bone and we believe that TPTD response is less affected by prior BP use in primarily cancellous sites (vs cortical sites). In addition, initial fracture healing is dependent on callus formation which is not diminished by BP. Furthermore, there was no significant difference in delayed union of the fractured bone between placebo and zoledronic acid after hip fracture. However, given the potential for recent BP use to alter BMD and turnover response to TPTD, we will stratify by BP use to ensure that any effect of BP on TPTD is equally distributed between the placebo and TPTD groups. In addition, we will record length and type of bisphosphonate use as a potential covariate in the analysis to evaluate effect modification by prior BP use.

**Open Label Extension:** After 3 months of placebo versus TPTD, when the data for the primary analysis of all aims has been collected, all persons will be offered to continue TPTD (open label) for 9 months while pain and physical performance are assessed and surveys completed every 3 months. The open label protocol will allow

for an evaluation of the persistence of any potential benefit of TPTD on fracture healing (assuming that one is evident after the first 3 months) on functional outcomes. We believe offering open label TPTD after the 3 months placebo controlled blinded trial will also help aid in the recruitment of patients since they will all eventually be treated and the extension follows guidelines to treat patients with pelvic fracture (consistent with severe osteoporosis). During the open label extension, the ~32% of the control group that may not have healed at 3 months will be followed with radiographs to enable us to determine the time to heal in this group. Treatment with open label TPTD may accelerate their healing and mitigate the difference in the secondary aim of functional outcomes between groups during the latter part of the year (3-12 months). However, we believe most of the effect on the secondary outcomes of physical function and pain would have occurred in the first 3 months for most people and modest changes will only occur in a few patients. We hypothesize that differences seen between PBO and TPTD groups at 3 months will persist when evaluated up to 12 months. This will be assessed as a group by time interaction. This extension will add to the data on pain and physical function collected at the end of the double blind trial (0 to 3 months). If the natural history cohort is large enough we would also be able to see if the TPTD over 3 months, with continued treatment for the subsequent 9 months improves physical function more than no treatment over the year. The open label extension will allow us to determine whether our hypothesis of faster healing by TPTD (at the end of 3 months) produces a long term benefit of improved function between 3 and 12 months, or if the effect wanes within that group. Evidence of a better result if TPTD is started immediately may enhance treatment rates post fracture.

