The primary outcome analysis is an ITT analysis of the categorization of the level of cortical bridging seen on focus CT at 3-months. The operational definition of cortical bridging is a five-level ordinal scale from "not healed" to "healed" (cf. protocol) adjudicated by the radiologists and clinicians, with two qualifications: 1) if endpoint assessment is missing because of a drop-out or loss-to-follow subsequent to an AE or SAE, the endpoint will be coded as "not healed"; 2) if the endpoint is missing for any other reason, the endpoint will be coded as the last available coding of the focus CT assessment. The treatment difference in cortical bridging will be evaluated by a 2x5 chi-square (group x score) with a trend test (Jonckheere-Terpstra) for the ordinal

level of bridging to see whether the TPTD treated participants “trend” to have a greater proportion of higher bridging scores than the placebo group.

Secondary analysis of the treatment group differences in the change in fracture healing scores across the 3-months of the placebo-controlled phase will use a generalized estimating equation for longitudinal repeated measures assuming a Poisson distribution with observation-level weighting from a logistic regression analysis of the missingness pattern following the approach used by Fitzmaurice, Lair and Ware (2011). The outcome will be coded as described for the primary outcome ITT analysis. Missing covariate values will be filled using the fully conditional specification multiple imputation method to impute a monotonically missing data pattern: outcomes will not be imputed. Continuous covariates will use the predictive mean matching method while classification covariates will use a logistic regression method.

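### Withdrawing subjects are not asked for the week-12 CT that defines the primary endpoint, and the value that stands in for it can bias the comparison in either direction

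*Combined protocol and SAP*

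**What the plan says.** The primary outcome is fracture healing on Focus CT at 3 months, analysed by intention to treat (Protocol Summary; Statistical Plan in section 7). For subjects still in the study, section 4 (Follow-up visits) provides the endpoint scan: "At 3 months the remaining patients who still have not healed will undergo a focused limited low dose CT". Before month 3, a Focus CT is done only if the monthly radiograph shows bridging.

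Subjects who leave the study fall under the Withdrawals paragraph of section 4. They are asked for a "final x-ray and focus CT if they consent and there has not been one within a month". No other paragraph asks them to come back at week 12.

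The Protocol Summary then says how the missing 3-month value is filled. After an adverse event it is coded not healed. For any other reason, "the endpoint will be coded as the last available coding of the focus CT assessment". The Statistical Plan, by contrast, says that missing outcomes will not be imputed.

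Section 4 (Recruitment) sets the sample size "to accommodate a drop-out rate of 20% in the 3 month treatment portion of the study". Section 3 gives the control course in a cited non-randomised study as "9% healed at 8 weeks and 68% at 12 weeks", and for the treated patients "100% of the treated group had healed at 8 weeks following PTH1-84 administration". The trial adopts these values: the Sample Size Justification uses 100% against 9% at week 8, and Open Label Extension expects about 32% of controls to be unhealed at 3 months.

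**The concern.** A scan up to a month old, or one taken at exit, is accepted as if it had been taken at week 12. On the protocol's own figures 59 of the 68 percentage points of control healing (87%) arise between weeks 8 and 12, so this is the month in which an older scan misleads most about a placebo patient. Subjects who leave earlier, or after an adverse event, are misrecorded in the TPTD arm as well. At stake is whether the primary comparison, for up to one patient in five, measures healing at week 12 or the timing and reason of withdrawal.

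**Working it through.** **Inputs.** 100 randomised 1:1, so 50 per arm; drop-out d = 20%; control healing 9% at week 8 and 68% at week 12; treated healing 100% at week 8 (section 3). The primary power calculation uses 60% for placebo at 3 months instead of 68%. The documents give no healing rate before week 8 and no split of withdrawals by reason, so both are varied below.

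**The plan's own figure.** With 40 per group, 60% against 100%, two-sided alpha 1% and mean proportion 0.80: z = (0.40 × √40 − 2.576 × √(2 × 0.80 × 0.20)) / √(0.60 × 0.40 + 0) = (2.530 − 1.457) / 0.490 = 2.19, which is 98.6% power. A Fisher exact enumeration gives 99.8%. Both agree with the stated power above 95%, and 80 / 0.80 = 100 agrees with the recruitment target. The planned size is not in question.

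**Formula.** Recorded healing in an arm = (1 − d) × p + d × s, where p is the week-12 rate and s is the share of withdrawals scored healed. With the same d in both arms, and withdrawals assumed to heal like completers in their arm:

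recorded gap − true gap = d × [(s for TPTD − s for placebo) − (p for TPTD − p for placebo)].

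With p = 100% and 68%, the bias is 0.20 × [(s for TPTD − s for placebo) − 32] points. Its sign depends only on whether the stand-in values differ between arms by more or less than 32 points.

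| Withdrawals (20% in each arm) | Placebo | TPTD | Gap | Bias |
|---|---|---|---|---|
| Week-12 CT obtained on all | 68% | 100% | 32 | 0 |
| None after an adverse event, week-8 CT carried forward | 0.8 × 68 + 0.2 × 9 = 56.2% | 100% | 43.8 | +11.8 |
| Half after an adverse event, half as in the row above | 54.4 + 0.1 × 9 = 55.3% | 80 + 10 = 90% | 34.7 | +2.7 |
| All scored not healed (adverse event, or early exit with no healing yet) | 54.4% | 80% | 25.6 | −6.4 |

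- **Break-even by reason.** Exits in weeks 8 to 12 give no bias when (1 − f) × 91 = 32, so f = 65% of them follow an adverse event. Above that share the bias is against TPTD.
- **Early exits without an adverse event.** If no placebo withdrawal is healed at the last CT, the bias is 0.20 × (h − 32), where h is the percentage of TPTD withdrawals healed at theirs. With h unknown, the range is −6.4 (h = 0) to +13.6 (h = 100), changing sign at h = 32.
- **With the 60% planning rate.** The second and last rows give +10.2 and −8.0 points against a true gap of 40; break-even is 56%.
- **With half the withdrawal.** At 10% the second row gives placebo (45 × 68 + 5 × 9) / 50 = 62.1%, a gap of 37.9 points.
- **No true effect.** If both arms go from 9% to 68%, equal withdrawal gives a bias of 0. With 25% placebo and 15% TPTD withdrawal the recorded rates are 53.25% and 59.15%, a difference of 5.9 points; swapping the rates reverses the sign.
- **Power of a healed/not-healed comparison, 50 per arm, two-sided alpha 1%.** 97.7% with week-12 scans on everyone; about 56% in the last row of the table.

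**Reach of the exemption.** The Withdrawals paragraph does not say whether the recent examination that waives the scan is the radiograph, the CT or both. Radiographs are monthly ("At every visit a pelvic radiograph will be taken"), so on that reading nearly every withdrawal is exempt, and a subject who never showed bridging may have no Focus CT to carry forward. If the CT is meant, the exempt subjects are those with some bridging at the previous visit. Leaving later does not help them: a subject who leaves at week 11 with a week-8 CT keeps the week-8 score.

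**The case against.** The case on the other side has five parts.

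- **The direction is not fixed.** A reader might infer that the rule favours TPTD and could produce a false positive. The documents do not support that. It holds for exits without an adverse event around weeks 8 to 12, on the assumed healing curves. Before then TPTD healing is under-recorded too, and the not-healed code costs TPTD more (100 to 0) than placebo (68 to 0). With no effect and equal withdrawal nothing is created. This part stands, and the conclusion is limited accordingly.
- **The inputs are weak.** The healing rates come from a study that section 3 itself calls open to bias and that used a different peptide, and the primary test is on an ordinal score with no expected distribution given. This stands as a limit on the size. It does not turn an exit scan into a week-12 scan.
- **The harm runs through the coding rule.** If the Statistical Plan's statement against imputation governs, carry-forward disappears. True, but withdrawals then drop out of the analysis and any bias depends on who leaves. A week-12 scan helps under either rule.
- **Stopping study drug is different from withdrawing.** A reader might infer that subjects who only stop the drug also miss the scan. The Withdrawals paragraph covers leaving the study, and the follow-up schedule has no exclusion for stopping drug, so this is silence that needs one clarifying sentence.
- **Deferring the scan could lose it.** A subject who agrees to return may not come. This stands, and it is why an exit scan must be kept as a fallback.

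**Conclusion.** The gap in the plan is real: subjects who withdraw are not asked for the examination that defines the primary endpoint, and an older scan or a code takes its place. The resulting bias can go either way. At the planned 20% drop-out and the protocol's 68% and 100%, the two main scenarios record 43.8 and 25.6 points against a true 32; the sign depends on the reason, timing and balance of withdrawal. The 43.8 is an upper-end case: it needs the whole 20% to be free of adverse events and scored on a week-8 CT. All figures assume that withdrawals would have healed like completers in their arm, and they describe healed/not healed, so they do not give the bias of the trend test on the 0 to 4 score. The change is worth making because an observed week-12 result removes the distortion in both directions.

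**What to change.** Amend the Withdrawals paragraph of section 4:

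- Ask any subject who withdraws and is not already documented as healed, with consent, for a radiograph and Focus CT at the scheduled week-12 date, whatever the date of the last scan.
- Take an exit scan where the subject is unlikely or unwilling to return.
- State that subjects who only stop study drug stay on the imaging schedule.

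In the Protocol Summary and Statistical Plan, say that a week-12 result, when obtained, is the endpoint regardless of the reason for withdrawal. Reconcile the coding rules for missing endpoints with the statement that outcomes are not imputed. A sensitivity analysis by reason and time of withdrawal would show how far the remaining missing values matter.

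The cost is one amended paragraph and matching wording in the analysis text. Some subjects who agree will not return. Those now exempt have one more low-dose scan, which other unhealed subjects already receive at 3 months; a subject scanned at exit who does return also has one extra.
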